9.3. Efficacy Analysis

Tumor response will be presented in the form of patient data listings that include, but are not limited to, tumor type, starting dose, tumor response at each visit, and best overall response (and PSA50 response if prostate cancer patient). In addition, progression date, death date, date of first response and last tumor assessment date, and date of last contact will be listed. Objective response rate (ORR), progression-free survival (PFS), overall survival (OS), Time to Response (TTR), time to progression (TTP), duration of response (DoR), and PSA50 response rate for prostate cancer patients will be summarized and presented if data permits. For these efficacy parameters, all dose levels and tumor types will be included for part 1 patients, for part 2 patients, summary will be for mCRPC patients.

The definition of each response category is provided in the Appendix for RECIST 1.1.

9.4. Analysis of Pharmacokinetics CCl

9.4.1. Analysis of Pharmacokinetics

9.4.1.1. Single-Dose and Steady-State PF-06952229 Pharmacokinetic Analysis

Plasma PK parameters including the maximum plasma concentration (C_{max}), time to maximum plasma concentration (T_{max}), and area under the plasma concentration versus time curve (AUC_{last}) for PF-06952229 will be estimated using noncompartmental analysis. If data permit or if considered appropriate, area under the plasma concentration versus time curve from time 0 extrapolated to infinity (AUC_{inf}), terminal elimination half-life ($t_{1/2}$), apparent oral plasma clearance (CL/F), apparent volume of distribution (V_{ss} /F or V_z /F), accumulation ratio (R_{ac}) and linearity ratio (R_{ss}) will be also estimated. The single-dose and steady-state PK parameters will be summarized descriptively (n, mean, standard deviation, coefficient of variation [CV], median, minimum, maximum, geometric mean and its associated CV) by dose, cycle and day.

For PF-06952229 concentrations, concentrations will be summarized descriptively (n, mean, standard deviation, CV, median, minimum, maximum, geometric mean and its associated

CV) by dose, cycle, day and nominal time. Individual patient and median profiles of the concentration-time data will be plotted by dose, cycle and day (single dose and steady state) using nominal times. Individual and median profiles will be presented on both linear-linear and log-linear scales.

Dose normalized AUC_{last} and C_{max} will be plotted against dose (using a logarithmic scale) by cycle and day. These plots will include individual patient values and the geometric means for each dose. These plots will be used to help understand the relationship between the PK parameters and dose.

The observed accumulation ratio and the linearity ratio will be summarized descriptively. Each will be analyzed after natural log transformation using a one-way analysis of variance (ANOVA) with a single term for dose. The means and 90% confidence intervals (CIs) obtained from the model will be back-transformed to provide means and 90% CIs for the accumulation and linearity ratios for each dose.

Trough concentrations will be plotted for each dose using a box-whisker plot by cycle and day within cycle in order to assess the attainment of steady state.

Urine PK parameters (Ae%, CL_R) for PF-06952229 will also be estimated and summarized.

9.5. Safety Analysis

Summaries and analyses of safety parameters will include all patients in the Safety Analysis Set.

9.5.1. Analysis of the Primary Endpoint

DLT is a primary endpoint of the dose escalation components of the study. The occurrence of DLTs observed in the dosing cohorts is used to estimate the MTD as described in the Study Design section. Adverse Events constituting DLTs will be listed per dose level.

9.5.2. Analysis of Secondary Safety Endpoints

Adverse Events

AEs will be graded by the investigator according to the CTCAE version 5.0 and coded using the Medical Dictionary for Regulatory Activities (MedDRA). The focus of AE summaries will be on Treatment Emergent Adverse Events, those with initial onset or increasing in severity after the first dose of study treatment. The number and percentage of patients who experienced any AE, SAE, treatment related AE, and treatment related SAE will be summarized according to worst toxicity grades. The summaries will present AEs both on the entire study period and by cycle (Cycle 1 and Cycles beyond 1).

Laboratory Test Abnormalities

The number and percentage of patients who experienced laboratory test abnormalities will be summarized according to worst toxicity grade observed for each laboratory assay. The analyses will summarize laboratory tests both on the entire study period and by cycle (Cycle 1 and Cycles beyond 1). Shift tables will be provided to examine the distribution of laboratory toxicities.

For laboratory tests without CTCAE grade definitions, results will be categorized as normal, abnormal, or not done.

9.5.3. Electrocardiogram

The analysis of ECG results will be based on patients in the safety analysis set with baseline and on treatment ECG data.

ECG measurements (an average of the triplicate measurements) will be used for the statistical analysis and all data presentations. Any data obtained from ECGs repeated for

safety reasons after the nominal time points will not be averaged along with the preceding triplicates. Interval measurements from repeated ECGs will be included in the outlier analysis (categorical analysis) as individual values obtained at unscheduled time points.

QT intervals will be corrected for heart rate (QTc) using standard correction factors (ie, Fridericia's (default correction), Bazett's, and possibly a study specific factor, as appropriate). Data will be summarized and listed for QT, heart rate, RR and PR interval, QRS, QTcF (and other correction factors, eg, QTcB as appropriate). Individual QT (all evaluated corrections) intervals will be listed. The most appropriate correction factor will be selected and used for the following analyses of central tendency and outliers and used for the study conclusions. Descriptive statistics (n, mean, median, standard deviation, minimum, and maximum) will be used to summarize the absolute corrected QT interval and changes from baseline in corrected QT after treatment, dose and time point. For each patient and by treatment, the maximum change from baseline will be calculated as well as the maximum post baseline interval across time points. Categorical analysis will be conducted for the maximum change from baseline in corrected QT and the maximum post baseline QT interval.

Shift tables will be provided for baseline vs worst on treatment corrected QT (one or more correction methods will be used) using maximum CTCAE Grade. Shift tables will also be provided for ECG abnormality at baseline vs on treatment (yes, no, not done: (n, %)). Patients experiencing clinically relevant morphological ECG changes will be summarized (including frequency and percentage).

The effect of drug concentrations on corrected QT change from baseline will be explored graphically. Additional concentration corrected QT analyses may be performed. Data may be pooled with other study results and/or explored further with PK/PD models.

9.6. Sample Size Determination

9.6.1. Part 1

In Part 1, patients will participate in a dose escalation phase aimed at estimating the MTD. The sample size for this component of the study will vary depending on the number of DLTs observed.

A maximum of 60 patients are expected to be enrolled in the dose escalation safety cohorts in Part 1, including approximately 40 patients for the monotherapy dose escalation and approximately 20 patients for the combination dose escalation. The actual number of patients enrolled will depend on the tolerability of PF-06952229 and the number of dose levels required to identify the MTD/RP2D. It is expected that the dose escalation process can be stopped and MTD declared with approximately 6 to 12 patients at the MTD dose. As for the number of patients treated at each dose, it is expected to be at 1 to 4 patients for the doses actually studied. However, since variable cohort size is allowed, the actual number of patients treated at each dose (including MTD) will vary from 1 to 12 patients.

9.6.2. Part 2

For PF-06952229 single agent expansion in patients with mCRPC, the planned sample size of the expansion cohort is 10 based on clinical consideration.

PF-06952229 single agent in combination with enzalutamide for patients with metastatic castration-resistant prostate cancer (mCRPC), assuming a sample size of 20, and the observed PSA50 response is 60% (12/20), the Bayesian posterior probability to demonstrate that the "True PSA50 response" is greater than 37% is 98.15%. Assuming 80% of the 20 patients have measurable disease and are response evaluable (16 patients evaluable), and the observed ORR is 43.75% (7/16), the Bayesian posterior probability to demonstrate that the "True ORR" is greater than 30% is 86.89%.

All the Bayesian calculations above assume a non-informative Uniform (0,1) prior

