4.4. Modified Intent to Treat (mITT) Population

The modified intent to treat (mITT) is the analysis population that will follow the ITT principle and include patients receiving at least 1 dose of investigational product with baseline assessment and at least 1 post baseline assessment, disease progression, or death before the first tumor assessment. The mITT population will be used for analyses and to support conference presentations when the study is still ongoing.

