5.2.3. Sample Size Determination

Part 1

In Part 1, patients will participate in a dose escalation phase aimed at estimating the MTD. The sample size for this component of the study will vary depending on the number of DLTs observed.

A maximum of 60 patients are expected to be enrolled in the dose escalation safety cohorts in Part 1, including approximately 40 patients for the monotherapy dose escalation and approximately 20 patients for the combination dose escalation. The actual number of patients enrolled will depend on the tolerability of PF 06952229 and the number of dose levels required to identify the MTD/RP2D. It is expected that the dose escalation process can be stopped and MTD declared with approximately 6 to 12 patients at the MTD dose. As for the number of patients treated at each dose, it is expected to be at 1 to 4 patients for the doses actually studied. However, since variable cohort size is allowed, the actual number of patients treated at each dose (including MTD) will vary from 1 to 12 patients.

Part 2

For PF 06952229 single agent expansion in patients with mCRPC, the planned sample size of the expansion cohort is 10 based on clinical consideration.

PF 06952229 single agent in combination with enzalutamide for patients with metastatic castration resistant prostate cancer (mCRPC), assuming a sample size of 20, and the observed PSA50 response is 60% (12/20), the Bayesian posterior probability to demonstrate that the "True PSA50 response" is greater than 37% is 98.15%. Assuming 80% of the 20 patients have measurable disease and are response evaluable (16 patients evaluable), and

the observed ORR is 43.75% (7/16), the Bayesian posterior probability to demonstrate that the "True ORR" is greater than 30% is 86.89%.

All the Bayesian calculations above assume a non informative Uniform (0,1) prior.

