5.3.2. Analyses for Binary Data

Binary endpoints in this study include ORR, complete response (CR), and partial response (PR). Response assessment will be based on PCWG2 for prostate cancer patient, and will use RECIST 1.1 for other tumor types. If deemed necessary disease control rate (ie, DCR, which is defined as the proportion of patients that achieved CR, or PR, or stable disease) may also be calculated for Part 2. Descriptive statistics along with the corresponding 2-sided 95% confidence intervals using an exact method will be provided for these endpoints.

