6. ANALYSES AND SUMMARIES

For efficacy related endpoints in this study, the following analysis plan may be implemented if the data is sufficient. For tumor response assessment, PCWG2 will be used for prostate cancer patient and RECIST 1.1 will be used for other tumor types.

Endpoint	CCI	Part 2
ORR		Both
PFS		Unconfirmed*
DOR		Both
TPP		Unconfirmed*
TTR		Both

Note: "Both" in the above table represents both unconfirmed and confirmed tumor assessments.

*: Confirmation for progressed disease is not applicable in RECIST 1.1.

In the "unconfirmed" analyses (ie, tumor response or progression without confirmation required), all tumor assessments data will be included for analyses. Specifically, regardless if a patient's tumor response or progression is subsequently confirmed or not, the patient data will all be included in the "unconfirmed" analyses. This is a more comprehensive analysis where tumor confirmation is not required and not taken into account. For example in the ORR analysis, if a patient achieved CR or PR, regardless it is subsequently confirmed or not, the patient will be included in the numerator.

In the "confirmed" analyses (ie, tumor response with confirmation required), only those tumor assessments data that's subsequently confirmed by a consecutive tumor scan will be considered as a "success" or "event" and be included for analyses as appropriate. For example, in the ORR analysis, a patient will only be counted in the numerator (the "success") if the tumor response (CR or PR) is subsequently confirmed. If a patient's tumor response is not subsequently confirmed, the patient will still be included in the denominator (the population set) but will not be included in the numerator (the "success").

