6.3. Analysis for Secondary Endpoints

6.3.1. Efficacy Endpoints Analysis

ORR, as assessed using PCWG2 for prostate cancer and RECIST version 1.1 for other tumor types, is a key efficacy endpoint. The following analyses will be performed in the mITT population by tumor type and pooled:

The ORR, along with other efficacy analyses will be performed in the mITT population. Part 1 and Part 2 data will be summarized separately, and may also be pooled together for analysis if deemed necessary. Specifically, the key tables in Part 2 include:

1. ORR by visit: investigator provided tumor response CR, PR, and CR+PR will be presented by descriptive statistics (frequency and percentage) and 95% confidence interval.
2. Best overall response of CR, PR, and CR+PR. This will include best overall response derivation without confirmation and with confirmation. Descriptive statistics (frequency and percentage) and 95% confidence interval will be provided.

Tumor response data in Part 1, Part 2 and across the two Parts may be summarized with descriptive statistics (frequency and percentage) in the following groups by visit and then best overall response across all visits:

- Overall summary for all doses and all tumor types;
- By tumor type regardless of dose;
- By dose regardless of tumor type;
- By dose and tumor type if data permit.

Summary tables of best overall response rate, PFS, OS, DOSD, and DOR may be provided by the groups aforementioned when deemed necessary (eg, if there are ≥ 5 patients in a specific group).

In addition, PSA50 Response Rate defined as $\geq 50\%$ PSA reduction from baseline assessed by PCWG2 for prostate cancer patients will be summarized similarly as ORR. See [Section 9.5](#) for more details on PSA measurement.

Efficacy listings (tumor measurements listings and tumor response listings) will be provided that include the investigator provided tumor measurement data, tumor response, best overall response, first CR/PR date, last date with CR or PR, most recent date without progression, progression date, death date, and last tumor assessment date, etc.

Endpoint	Analysis Set	Statistical Method	Model/Covariates/Strata	Missing Data
Overall response	mITT	Exact CI	See aforementioned summary descriptions on data pooling across dose and tumor type	Observed case
Overall Survival	ITT	Kaplan-Meier	See aforementioned summary descriptions on data pooling across dose and tumor type	Censored at last visit

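### The Part 2B posterior probabilities do not follow from the stated Uniform(0,1) prior (ORR printed as 86.89%, recomputed as 89.54%), and the ORR illustration uses a different denominator from the planned ORR analysis

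*Protocol*

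**What the plan says.** Protocol 9.6.2 and SAP 5.2.3 carry the same sample-size text for Part 2B. With 12 PSA50 responders among 20 patients, the probability that the true PSA50 rate exceeds 37% is given as 98.15%. For ORR the SAP writes: "Assuming 80% of the 20 patients have measurable disease and are response evaluable (16 patients evaluable". With 7 responders among those 16, the Protocol prints that the true ORR "is greater than 30% is 86.89"%. The Protocol closes with "All the Bayesian calculations above assume a non-informative Uniform (0,1) prior", and the SAP says the same.

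On the analysis side, SAP 6.3.1 states: "The ORR, along with other efficacy analyses will be performed in the mITT population". SAP 4.4 defines that population to "include patients receiving at least 1 dose of investigational product with baseline assessment and at least 1 post baseline assessment, disease progression, or death"; a death qualifies when it precedes any on-study scan. SAP 6 adds that when a response is not confirmed, "the patient will still be included in the denominator (the population set) but will not be included in the numerator". SAP 5.3.2 plans exact two-sided 95% confidence intervals for ORR. SAP 5.1 states that the study has no hypotheses.

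**The concern.** There are two separate problems in the same paragraph.

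First, the stated prior and the printed probabilities disagree. A reader who applies Uniform(0,1) to the printed counts gets different numbers, and the gap for ORR is too large to be rounding in a figure given to two decimals.

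Second, the ORR illustration is conditional on 16 patients who have measurable disease and can be evaluated for response. The mITT definition asks for neither. Inclusion criterion 3 (Protocol 4.1) accepts progression by measurable disease, by new bone lesions or by rising PSA, and it does not require measurable disease. The plan's own 80% assumption implies that about 4 of the 20 patients fall outside the 16. Under SAP 4.4 those patients can still count in the ORR denominator.

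These two probabilities are the only quantitative support offered for the 20-patient cohort; the Part 2A size is said to rest on clinical consideration. Estimating combination efficacy is a primary objective of Part 2B. If nothing changes, an ORR reported on up to 20 patients may be read against a planning figure built on 16.

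**Working it through.** **Inputs** (Protocol 9.6.2 and SAP 5.2.3): PSA50 x = 12, n = 20, threshold 0.37; ORR x = 7, n = 0.80 × 20 = 16, threshold 0.30; prior Uniform(0,1), which is Beta(1,1).

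**Formula.** With a Beta(a,b) prior the posterior is Beta(x+a, n−x+b), and the quantity wanted is its upper tail beyond the threshold p0. For integer parameters, P(Beta(A,B) > p0) = P(Bin(A+B−1, p0) ≤ A−1).

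**Step 1: reproduce the printed figures.** They appear when a = b = 0:

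- ORR: P(Beta(7,9) > 0.30) = P(Bin(15, 0.30) ≤ 6) = 0.86886, printed as 86.89%.
- PSA50: P(Beta(12,8) > 0.37) = P(Bin(19, 0.37) ≤ 11) = 0.98153, printed as 98.15%.

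Both match to the last printed digit. Solving for the single Beta(a,b) prior that returns both printed values gives a and b of about 0.01, in effect zero.

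**Step 2: apply the stated prior** (a = b = 1):

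- ORR: P(Beta(8,10) > 0.30) = P(Bin(17, 0.30) ≤ 7) = 0.89536, so 89.54%. Gap: 89.54 − 86.89 = 2.65 points.
- PSA50: P(Beta(13,9) > 0.37) = P(Bin(21, 0.37) ≤ 12) = 0.98214, so 98.21%. Gap: 98.21 − 98.15 = 0.06 point.

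A Beta(0.5, 0.5) prior, which the plan uses for DLTs in the MTD sections, gives 0.88294 and 0.98181 and matches neither printed value.

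**Step 3: let the ORR denominator grow.** Assumption: the number of responders stays at 7, the prior is Uniform(0,1), and n − 16 non-responding patients from outside the 16 enter mITT.

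| Patients in denominator | ORR estimate | P(ORR > 30%) |
|---|---|---|
| 16 | 43.75% | 89.54% |
| 17 | 41.2% | 85.93% |
| 18 | 38.9% | 81.80% |
| 19 | 36.8% | 77.23% |
| 20 | 35.0% | 72.30% |

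The n = 20 row assumes that all 20 patients enter mITT and none of the other four responds. A patient with non-target disease only can still reach CR, though not PR (table in SAP 9.5). If one of the four does so, 8/20 = 40.0% and the posterior is 85.24%.

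**Step 4: what the SAP would report**, with the exact 95% interval:

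- 7/16 = 43.75% (19.8% to 70.1%)
- 7/20 = 35.0% (15.4% to 59.2%)
- 8/20 = 40.0% (19.1% to 64.0%)

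With 7 responders, the choice of denominator alone can move the estimate by up to 43.75 − 35.0 = 8.75 points.

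**The case against.** The best case against acting is that little depends on these figures. N = 20 is an input to the calculation, not a result of it. There are no hypotheses, no decision rule uses the probabilities, and the SAP reports exact intervals, not posteriors. Only one of the two numbers is off by more than a trivial amount; it concerns ORR, a secondary endpoint in Part 2B, and the error understates the probability. All of this stands and limits the consequence. It does not make the printed numbers correct under the stated prior.

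The denominator point also meets several objections:

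- The SAP 9.5 statement on eligibility is about how progression is shown, so a patient entering on PSA or bone progression may still have measurable lesions. That is true of the sentence, but inclusion criterion 3 does not require measurable disease, and the 80% assumption already allows for patients outside the 16.
- SAP 9.5 introduces the non-target-only table with a garbled sentence that seems to treat such enrolment as a protocol deviation. Even on that reading, the mITT definition does not remove these patients.
- The SAP 6.3.1 table gives observed case as the missing-data rule for overall response. A patient with non-target disease only has a defined response status, so the data are not missing.
- The SAP 6 wording on the denominator addresses unconfirmed responses, not measurability. That is fair, but it still says that the denominator is the analysis population.
- The table for n = 17 to 20 holds responders at 7. That is an assumption made here, so those rows show sensitivity and do not predict a result.

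Finally, response listings are planned and the SAP allows added exploratory analyses, so a measurable-disease ORR could be built later. A prespecified summary would avoid having to choose the denominator after the data are seen.

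**Conclusion.** Both parts hold. The size of the numerical error is certain, because it follows from the printed counts and prior alone. The likely cause is equally clear: the prior's added success and failure were omitted, which is the only simple reading that returns both printed values from the printed counts.

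The denominator mismatch is also real, but its size cannot be fixed in advance. It depends on how many patients without measurable or evaluable disease enter mITT and whether any of them reaches CR. Under the plan's own 7 responders it ranges from no effect, if mITT contains only the 16, to the 20-patient case above.

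This should be corrected, but it does not threaten the design. The cohort size, the conduct of the trial and the planned intervals are unaffected.

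**What to change.** 1. In Protocol 9.6.2 and SAP 5.2.3, restate the probabilities as 89.54% (ORR) and 98.21% (PSA50) under Uniform(0,1). Alternatively keep the printed values and name the prior that produced them.
2. Align the ORR denominator in one of two ways. Either add to SAP 6.3.1 an ORR summary in mITT patients with measurable disease at baseline, shown beside the mITT ORR; or restate the illustration on the mITT denominator, giving the assumed mITT size and the assumed responders among patients without measurable disease.
3. Keep patients without measurable disease in the other planned analyses (PSA50, PFS, TTP, OS).

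The cost is two numbers in each document, plus either one summary row in the SAP or one reworded sentence in each document. Data collection and N = 20 do not change. The drawback of the added summary is that it rests on about 16 patients and will have a wide interval, as the 7/16 example shows.
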